## **5.1.3.1.** Injection Site Reactions

Injection site inflammation is expected following the second and subsequent injections of CMP-001. If subjects develop inflammation at the injection site, this may be managed using cold compresses and medications for pain and inflammation, such as acetaminophen or non-steroidal anti-inflammatory agents. If, in the Investigator's opinion, a tumor cannot be

injected due to injection site reaction or pain, refer to Section 5.1.2.3.1 on changing the site of injection.

[figure not shown]
## 5.1.3.2. Management of Adverse Events Associated with CMP-001

CMP-001 has been associated with a variety of flu-like symptoms and hypotension.

These symptoms could include fever, nausea, vomiting, chills, rigors, or hypotension. Additionally, symptoms such as headache, tachycardia, rash, and hypoxia may also occur. Symptoms should be expected within 1 to 4 hours following the injection but may also occur outside this window. Required prophylaxis is outlined in Section 5.1.2.1 to prevent or minimize the severity of these symptoms. If hypotension is unresponsive to IV fluids, stress dose steroids should be administered. The following algorithm (Figure 2) is provided as guidance for the treatment of symptoms associated with CMP-001.

For subjects who experience a Grade 3 or higher symptom deemed related to CMP-001, prophylaxis with stress dose steroids (prednisone 25 mg or equivalent at the Investigator's discretion) is recommended for subsequent CMP-001 doses.

Figure 2: Suggested Prophylaxis and Treatment for Symptoms Associated with CMP-001

Abbreviations: IV = intravenously; NSAID = nonsteroidal anti-inflammatory drug; po/PO= orally; Q4-6H = every 4-6 hours.

# 5.1.4. Dose Modifications and Management of Adverse Events Associated with Nivolumab

Nivolumab has been associated with a variety of AEs. The current nivolumab Investigator's Brochure should be consulted for treatment guidance on dose modifications.

If a planned nivolumab dosing is delayed, the CMP-001 dosing may also be delayed. When nivolumab is permanently discontinued because of an immune-related AE, CMP-001 must also be permanently discontinued.

A pattern of immune-related AEs has been defined for nivolumab, for which management algorithms have been developed; these are provided in Appendix H. Most high-grade events were manageable with the use of corticosteroids or hormone replacement therapy (endocrinopathies) as instructed in these algorithms.

Nivolumab administration should be delayed or discontinued as specified in Table 2.

Table 2: Dose Modifications and Management of Adverse Events Associated with Nivolumab

Drug-Related Adverse Event	Severity a	Action Taken	Clarifications, Exceptions, and Resume Criteria
Colitis or diarrhea	Grade 2	Delay dose b	Dosing may resume when AE resolves to Baseline.
	Grade 3	Delay dose b when administered as a single agent	Dosing may resume when AE resolves to Baseline.
	Grade 4	Permanently discontinue	
Serum Creatinine Increased	Grade 2 or 3	Delay dose b	Dosing may resume when AE resolves to Grade ≤ 1 or Baseline value.
	Grade 4	Permanently discontinue	
Pneumonitis	Grade 2	Delay dose b	Dosing may resume after pneumonitis resolves to Grade ≤ 1 or Baseline value.
	Grade 3 or 4	Permanently discontinue	
Aspartate aminotransferase (AST), alanine aminotransferase (ALT), or total bilirubin (T.bili) increased	AST or ALT > $3x$ and $\le 5x$ upper limit of normal (ULN) or T.Bili > $1.5 x$ and $\le 3 x$ ULN, regardless of Baseline value	Delay dose b	Dosing may resume when laboratory values return to Baseline.
	AST or ALT > 5 x ULN or T. bili >3 x ULN, regardless of Baseline value	Delay dose b or permanently discontinue (see clarification)	In most cases of AST or ALT > 5 x ULN, study treatment will be permanently discontinued. If the Investigator determines a possible favorable benefit/risk ratio that warrants continuation of study treatment, a discussion between the Investigator and the Medical Monitor/ designee must occur and

Drug-Related Adverse Event	Severity a	Action Taken	Clarifications, Exceptions, and Resume Criteria
			approval from Medical Monitor prior to resuming therapy.
Adrenal Insufficiency	Grade 2 adrenal insufficiency	Delay dose b	Dosing may resume after adequately controlled with hormone replacement.
	Grade 3 or 4 adrenal insufficiency or adrenal crisis	Delay dose b or permanently discontinue	Mandatory discussion with and approval from the Medical Monitor needed prior to resuming therapy. If adrenal insufficiency resolves or is adequately controlled with physiologic hormone replacement, participant may not require discontinuation of study drug.
Hyperglycemia	Grade 2 or 3 (Hyperglycemia requiring initiation or change in daily management)	Delay dose b	Dosing may resume if hyperglycemia resolves to Grade ≤ 1 or Baseline value, or is adequately controlled with glucosecontrolling agents.
	Grade 4	Permanently discontinue	Mandatory discussion with and approval from the Medical Monitor needed prior to resuming therapy. If hyperglycemia resolves, or is adequately controlled with glucose-controlling agents, participant may not require discontinuation of study drug.
Hypophysitis/ Hypopituitarism	Symptomatic Grade 1 to 3 that is also associated with corresponding abnormal lab and/or pituitary scan	Delay dose b	Dosing may resume if endocrinopathy resolves to be asymptomatic, or is adequately controlled with only physiologic hormone replacement.
	Grade 4	Delay dose b or permanently discontinue	Mandatory discussion with and approval from the Medical Monitor needed prior to resuming therapy. If endocrinopathy resolves or is adequately controlled with physiologic hormone replacement, participant may not require discontinuation of study drug.
Hyperthyroidism or Hypothyroidism	Grade 2 or 3	Delay dose b	Dosing may resume if endocrinopathy resolves to be asymptomatic, or is adequately controlled with only physiologic hormone replacement or other medical management.
	Grade 4	Delay dose b or permanently discontinue	Mandatory discussion with and approval from the Medical Monitor needed prior to resuming therapy. If endocrinopathy resolves or is adequately controlled with physiologic hormone replacement

Drug-Related Adverse Event	Severity a	Action Taken	Clarifications, Exceptions, and Resume Criteria
			or other medical management, participant may not require discontinuation of study drug.
Rash	Grade 2 rash covering > 30% body surface area or Grade 3 rash or suspected SJS, TEN, or DRESS	Delay dose b	Dosing may resume when rash reduces to $\leq 10\%$ body surface area. Dosing may resume if SJS, TEN, or DRESS is ruled out and rash reduces to is $\leq 10\%$ body surface area.
	Grade 4 rash or confirmed SJS, TEN, or DRESS	Permanently discontinue	
Guillain-Barre Syndrome (GBS)	Any Grade	Permanently discontinue	
Myasthenia Gravis (MG)	Any Grade	Permanently discontinue	
Encephalitis	Any Grade encephalitis	Delay dose b	After workup for differential diagnosis, (ie, infection, tumor-related), if encephalitis is not drug related, then dosing may resume when AE resolves.
	Any Grade drug- related encephalitis	Permanently discontinue	
Myelitis	Any Grade myelitis	Delay dose b	After workup for differential diagnosis, (ie, infection, tumor-related), if myelitis is not drug related, then dosing may resume when AE resolves.
	Any Grade drug- related myelitis	Permanently discontinue	
Neurological (other than GBS, MG, encephalitis, or myelitis)	Grade 2	Delay dose b	Dosing may resume when AE resolves to Baseline.
	Grade 3 or 4	Permanently discontinue	
Myocarditis	Symptoms induced from mild to moderate activity or exertion	Delay dose b	Dosing may resume after myocarditis has resolved.
	Severe or life threatening, with symptoms at rest or with minimal activity or exertion, and/or where intervention indicated.	Permanently discontinue	

Drug-Related Adverse Event	Severity a	Action Taken	Clarifications, Exceptions, and Resume Criteria
Pancreatitis: Amylase or Lipase increased	Grade 3 with symptoms	Delay dose b	Note: Grade 3 increased amylase or lipase without signs or symptoms of pancreatitis does not require dose delay. Dosing may resume when subject becomes asymptomatic.
	Grade 4	Permanently discontinue	
Uveitis	Grade 2 uveitis	Delay dose b	Dosing may resume if uveitis responds to topical therapy (eye drops) and after uveitis resolves to Grade ≤ 1 or Baseline. If subject requires oral steroids for uveitis, then permanently discontinue study drug.
	Grade 3 or 4 uveitis	Permanently discontinue	
Other drug-related AE (not listed above)	Grade 2 non-skin AE, except fatigue	Delay dose b	Dosing may resume when AE resolves to Grade ≤ 1 or Baseline value.
	Grade 3 AE - First occurrence lasting ≤ 7 days	Delay dose b	Dosing may resume when AE resolves to Grade ≤ 1 or Baseline value.
	Grade 3 AE- First occurrence lasting > 7 days	Permanently discontinue	
	Recurrence of Grade 3 AE of any duration	Permanently discontinue	
	Grade 4 or Life- threatening adverse reaction	Permanently discontinue	
Other drug-related laboratory abnormality (not listed above)	Grade 3	Delay dose b	Exceptions:  No delay required for: Grade 3 lymphopenia  Permanent Discontinuation for: Grade 3 thrombocytopenia > 7 days or associated with bleeding.
	Grade 4	Permanently discontinue	Exceptions: The following events do not require discontinuation of study drug:  • Grade 4 neutropenia ≤ 7 days  • Grade 4 lymphopenia or leukopenia  • Grade 4 isolated electrolyte imbalances/abnormalities that are not associated with clinical sequelae and are responding to supplementation/appropriate

Drug-Related Adverse Event	Severity a	Action Taken	Clarifications, Exceptions, and Resume Criteria
			management within 72 hours of their onset.
Hypersensitivity reaction or infusion reaction (manifested by fever, chills, rigors, headache, rash, pruritus, arthralgia, hypotension, hypertension, bronchospasm, or other allergic-like reactions)	Grade 3 or 4	Permanently discontinue	Refer to Section 5.1.4.2. on Treatment of Related Infusion Reactions.

Abbreviations: ALT = alanine aminotransferase; AST = aspartate aminotransferase; DRESS = drug reaction with eosinophilia and systemic symptoms; SJS = Stevens-Johnson syndrome; TEN = toxic epidermal necrolysis; ULN = upper limit of normal.

Nivolumab dosing should also be delayed for any AE, laboratory abnormality, or intercurrent illness which, in the judgment of the Investigator, warrants delaying the dose of study medication.

Any event that leads to delay in dosing lasting > 12 weeks from the previous dose requires discontinuation, with the following exceptions:

- Dosing delays to allow for prolonged steroid tapers to manage drug-related AEs are allowed.
- Dosing delays lasting > 12 weeks from the previous dose that occur for non-drugrelated reasons may be allowed if approved by the Medical Monitor (or designee).

Subjects who require delay of nivolumab should be re-evaluated weekly or more frequently if clinically indicated and resume nivolumab dosing when re-treatment criteria are met (see Section 5.1.4.1). Tumor assessments should continue as per protocol even if dosing is delayed.

A pattern of immune-related AEs has been defined, for which management algorithms have been developed; these are provided in Appendix H. Most high-grade events were manageable with the use of corticosteroids or hormone replacement therapy (endocrinopathies) as instructed in these algorithms.

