#### 5.1.4.1. Criteria to Resume Nivolumab Treatment

Please see Table 2 for guidance on resuming treatment.

Tumor assessments should continue as per protocol even if dosing is delayed. Periodic study visits to assess safety and laboratory studies should also continue every 6 weeks or more frequently if clinically indicated during such dosing delays.

a Toxicity was graded per National Cancer Institute Common Terminology Criteria for Adverse Events Version 5.0.

b Resume treatment when adverse reaction improves to Grade 0 or 1.

<sup>c Resume treatment when AST/ALT returns to Baseline.

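### Table 2 puts a general Grade 0-or-1 resume rule on five drug-related delay entries whose last column asks for Baseline or resolution, and no text says which governs

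*Protocol*

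**What the plan says.** Section 5.1.4 sends the site to Table 2 for when to delay or stop nivolumab, and to the Investigator's Brochure for guidance on dose modification. Every delay action in the table carries marker b, and footnote b reads "Resume treatment when adverse reaction improves to Grade 0 or 1".

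The last column of the same table is headed "Clarifications, Exceptions, and Resume Criteria". In five drug-related delay entries it sets its own condition:

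- Colitis or diarrhea Grade 2, and Grade 3 when nivolumab is given as a single agent: "Dosing may resume when AE resolves to Baseline".
- AST or ALT above 3 and up to 5 times ULN, or bilirubin above 1.5 and up to 3 times ULN (the lower liver band): "Dosing may resume when laboratory values return to Baseline".
- Neurological events other than those listed separately, Grade 2: the same sentence as for colitis.
- Myocarditis with symptoms on mild to moderate activity: "Dosing may resume after myocarditis has resolved".

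Footnote c reads "Resume treatment when AST/ALT returns to Baseline", but no entry shows a marker c in the text as read. The paragraph after the table tells the site to resume once re-treatment criteria are met and refers to Section 5.1.4.1. That section says "Please see Table 2 for guidance on resuming treatment".

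**The concern.** The same entry gives two resume rules. Footnote b is not worded as a fallback: it is a plain instruction, marked directly on the action the site is about to take. For these five entries the last column gives a different instruction. The protocol does not say that one overrides the other.

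This is a rule that sites act on. Under footnote b, a subject whose colitis, liver tests or neurological event has come down to Grade 1 but not to Baseline may be given nivolumab again. Under the row text, that subject must wait. Reading the row has its own cost: Section 5.1.4 requires discontinuation when a delay exceeds 12 weeks from the previous dose, with stated exceptions. Two sites could therefore handle the same event differently, one re-exposing early and the other waiting longer.

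**Working it through.** No formula applies. The check is a hand count of Table 2 and a side-by-side reading.

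**Step 1. Count the delay entries that carry marker b**, in table order:

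- Colitis (2), creatinine (1), pneumonitis (1), liver (2) = 6
- Adrenal (2), hyperglycemia (1), hypophysitis (2), thyroid (2) = 7
- Rash, encephalitis, myelitis, neurological Grade 2, myocarditis, pancreatitis, uveitis, other event Grade 2 = 8
- Other event Grade 3 (first occurrence, up to 7 days), other laboratory abnormality Grade 3 = 2

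Total: 6 + 7 + 8 + 2 = 23.

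**Step 2. Sort them by what the last column asks.**

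| Last column | Entries | Count |
|---|---|---|
| Baseline or resolution, drug-related event | Colitis Grade 2, colitis Grade 3, lower liver band, neurological Grade 2, myocarditis | 5 |
| Resolution, only if the event is not drug-related | Encephalitis, myelitis | 2 |
| Grade 1 or less, or Baseline | Creatinine, pneumonitis, hyperglycemia (or control on medication), uveitis (with response to topical therapy), other event Grade 2, other event Grade 3 | 6 |
| Another kind of criterion (hormone control, absence of symptoms, body surface area, Medical Monitor approval) | Adrenal ×2, hypophysitis ×2, thyroid ×2, rash, pancreatitis | 8 |
| Approval without a laboratory threshold | Upper liver band | 1 |
| None stated | Other laboratory abnormality Grade 3 | 1 |

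Check: 5 + 2 + 6 + 8 + 1 + 1 = 23.

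**Step 3. Are the two thresholds the same thing?** The table treats them as different. Six entries offer Grade 1 or Baseline as alternatives, and the five entries at issue leave the Grade 1 alternative out.

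**Step 4. Which is stricter?** It depends on where the subject started.

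- Baseline better than Grade 1: the row is stricter. Footnote b allows dosing at a residual Grade 1 event and the row does not.
- Baseline already Grade 1: for a clinically graded event the two coincide. For a laboratory value the row can still be tighter, since a value may sit within Grade 1 and above its Baseline.
- Baseline worse than Grade 1: the row would be the looser rule.

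The last two cases cannot be dismissed. Inclusion criterion 4 admits AST and ALT up to 3 times ULN, and bilirubin up to 3 times ULN with Gilbert disease. Exclusion criterion 6 tolerates residual Grade 1 events from earlier treatment. Appendix C gives only generic grade descriptions, so the documents do not show which grade a given liver value falls in.

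**Step 5. Look for a tie-break.** The text after Table 2 points to Section 5.1.4.1, which points back to Table 2. The note to the hepatic algorithm in Appendix H refers back to the protocol's delay criteria. None of these ranks the footnote against the column.

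**The case against.** The best answer is that the table already settles the matter. Only the last column is labelled as holding exceptions and resume criteria, so the natural reading is that footnote b is the default and the row the specific rule. This carries weight and is why the point is minor. But the precedence is left to inference, and footnote b is marked on the very entries it would have to yield to.

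Three qualifications stand.

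- The row is not always stricter (step 4).
- Myocarditis is described by symptoms, not grade, and Appendix C says that some grades do not apply to some events. If myocarditis has no Grade 1, footnote b there amounts to Grade 0, and four entries conflict, not five.
- The colitis Grade 3 entry is limited to single-agent use, so it clearly reaches Arm B only.

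The Investigator's Brochure, which was not available, may state the intended threshold. That would help a site but would not make the table agree with itself.

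Some stronger readings are tempting and are not supported:

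- A reader might infer that the upper liver band (AST or ALT above 5 times ULN, or bilirubin above 3 times ULN) has a looser re-dosing standard than the milder band, because footnote b is the only threshold marked on it. The row says that most cases of AST or ALT above 5 times ULN end in permanent discontinuation. Continuing requires a favorable benefit/risk judgment, a discussion and Medical Monitor approval. Taken whole, that is the tighter control.
- A reader might count seven conflicts by adding encephalitis and myelitis. Those rows allow dosing again only when the event proves unrelated to drug, as in "if encephalitis is not drug related, then dosing may resume when AE resolves". Drug-related cases are permanently discontinued.
- A reader might treat the missing marker c as an error. A superscript may have been lost when the PDF was read, so it carries no weight here.
- A reader might suppose that subjects were re-dosed too early. Nothing in the documents shows this.

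**Conclusion.** The text is wrong as written, at low severity. Five of 23 delay entries carry a footnote that differs from their own last column (four if myocarditis has no Grade 1). In the usual case, where Baseline is better than Grade 1, the footnote is the looser rule and would permit re-dosing at a residual Grade 1 event above Baseline.

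The practical size cannot be computed, because the documents give no rate of residual Grade 1 events. It is bounded by the trial's size: SAP Section II.C reports 20 treated subjects and closed enrollment, and SAP Section II.F lets those on treatment continue to the 2-year limit. Both arms receive nivolumab, so the rule applies to both, apart from the single-agent qualifier on colitis Grade 3.

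There is no effect on sample size, endpoints or any analysis. The conclusion assumes that the markers and row text were read correctly from the PDF and that no document outside these two fixes the order of precedence.

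**What to change.** Reword footnote b along these lines: *Resume once the criterion in the last column is met; if that column gives none, resume once the reaction is down to Grade 0 or 1.*

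The five entries then follow their row text, as do encephalitis and myelitis. The entries with a Grade 1 or Baseline alternative, and those with another kind of criterion, follow what their rows already say. The Grade 3 entry for other laboratory abnormalities keeps the Grade 0-or-1 rule it needs, because its row states none. The upper liver band stays with its approval procedure.

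No change to footnote c and no Baseline requirement for the upper liver band is proposed. The documents support neither, and any numeric threshold there is a clinical choice for the medical team.

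The cost is one sentence, with no new data, visits or procedures. As a protocol change it needs ethics approval under Section 12.1, so it can go with any other amendment. It matters only while subjects remain on nivolumab.

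### In Protocol Table 2 the Grade 4 hyperglycemia row both orders permanent discontinuation and allows resumption, and footnote b differs from many (not all) row-level resume criteria

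*Protocol*

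**What the plan says.** Table 2 in Protocol Section 5.1.4 gives, for each drug-related event, a severity, an action, and a last column for clarifications, exceptions and resume criteria.

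**Grade 4 hyperglycemia.** The action is permanent discontinuation, with no delay option. The last column reads "Mandatory discussion with and approval from the Medical Monitor needed prior to resuming therapy" and continues "If hyperglycemia resolves, or is adequately controlled with glucose-controlling agents, participant may not require discontinuation of study drug".

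**Parallel endocrine rows.** Grade 3 or 4 adrenal insufficiency, Grade 4 hypophysitis and Grade 4 thyroid events carry almost the same clarification, which likewise ends by saying that the "participant may not require discontinuation of study drug". Their action cell is "Delay dose b or permanently discontinue".

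**Footnote b.** Attached to every delay action, it reads "Resume treatment when adverse reaction improves to Grade 0 or 1". Many rows state their own criterion; for colitis or diarrhea it is "Dosing may resume when AE resolves to Baseline".

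**Linked rule for CMP-001.** Section 5.1.4 adds: "When nivolumab is permanently discontinued because of an immune-related AE, CMP-001 must also be permanently discontinued". Section 4.5 bars re-treatment with a study drug once it has been permanently discontinued (for more than 12 weeks).

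**The concern.** A dose-modification table should lead two sites with the same subject to the same action. Here the Grade 4 hyperglycemia row supports two outcomes: nivolumab stops for good, or it may resume after approval. For many delayed events, the footnote and the row set different thresholds for restarting.

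The first conflict bears on permanent discontinuation, which cannot be reversed within the study. In Arm A it also decides whether CMP-001 stops, if the event is judged immune-related. The second bears mainly on the timing of resumption. Either can affect reported results: adverse events leading to discontinuation are a secondary endpoint, and the SAP tabulates treatment-emergent events leading to discontinuation and doses delayed or permanently withdrawn.

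**Working it through.** The plan gives no figure to reproduce. The check is a row-by-row reading of Table 2 against its footnotes, Section 4.5 and Section 5.1.4.1, with a count of cells.

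**Step 1: the hyperglycemia row against its neighbors**

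| Row | Action cell | Clarification cell |
|---|---|---|
| Adrenal insufficiency, Grade 3 or 4 | Delay or discontinue | Approval before resuming; discontinuation may be avoidable |
| Hypophysitis, Grade 4 | Delay or discontinue | Same |
| Thyroid, Grade 4 | Delay or discontinue | Same |
| Hyperglycemia, Grade 4 | Discontinue only | Same |

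In the first three rows the two cells fit together. In the fourth, the clarification sets terms for resuming a drug that the action cell has ended. Where the table elsewhere overrides a discontinuation order (other laboratory abnormality, Grade 4), it labels the list as exceptions. The hyperglycemia row has no such label.

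**Step 2: footnote b against each delay cell**

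Twenty-three cells carry footnote b.

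| Relation to Grade 0 or 1 | Cells | Count |
|---|---|---|
| Different criterion | Colitis/diarrhea (2), hepatic (2), adrenal (2), hyperglycemia Grade 2 or 3 (1), hypophysitis (2), thyroid (2), rash (1), encephalitis (1), myelitis (1), other neurological (1), myocarditis (1), pancreatitis (1) | 17 |
| Grade 1 or less or Baseline, plus a response condition | Uveitis Grade 2 | 1 |
| Essentially agrees | Creatinine, pneumonitis, other AE Grade 2, other AE Grade 3 lasting up to 7 days | 4 |
| No row-level criterion | Other laboratory abnormality Grade 3 | 1 |

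17 + 1 + 4 + 1 = 23.

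The hepatic cells need a qualification. Footnote c requires AST/ALT to return to Baseline, which matches the lower hepatic row for those tests. No marker for footnote c is visible in the extracted text, and it may have been lost in reading the PDF. Setting both hepatic cells aside leaves 17 − 2 = 15.

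**Step 3: how the 15 differ**

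- *Row stricter than footnote b.* Colitis/diarrhea and other neurological events require Baseline, and myocarditis requires resolution. Encephalitis and myelitis require resolution and a workup showing the event is not drug related. A subject with no diarrhea at Baseline who improves from Grade 2 to Grade 1 may resume under the footnote but not under the row.
- *Row looser or on another scale.* Grade 2 adrenal insufficiency may resume once controlled on replacement, with no grade stated. Grade 2 or 3 hyperglycemia accepts Grade 1 or less, Baseline, or adequate control. Rash uses body surface area, and pancreatitis uses absence of symptoms.
- *Footnote already met at onset.* Hypophysitis triggers a delay from symptomatic Grade 1, so footnote b is satisfied when that delay is ordered.

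**Step 4: is there a tie-breaker?**

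The text after Table 2 sends the reader to Section 5.1.4.1 for re-treatment criteria, and Section 5.1.4.1 sends the reader back to Table 2. Neither ranks footnote against row.

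**Step 5: scale**

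The SAP (Sample Size Status) reports 9 subjects in Arm A and 11 in Arm B. One subject classified differently moves an arm's discontinuation rate by 1/9 = 11.1 or 1/11 = 9.1 percentage points.

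**The case against.** The best defense of the hyperglycemia row is that it states a default and then an exception. The last column is headed to include exceptions, and the Grade 4 laboratory row has the same layout. That reading is possible, but the site must infer it: the text is not labelled as an exception, and three rows with near-identical text word the action differently.

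The defense of footnote b is that specific rules override general ones. Where the row is stricter, a subject who meets it will normally be at Grade 0 or 1 too, so both can be satisfied. This eases the stricter rows if everyone reads them so, but the protocol never states that order. It does not help the rows on a looser or different scale.

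A reader might also infer more than the text supports:

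- *That footnote b contradicts every row.* Four cells agree with it, and for AST/ALT footnote c supports the row.
- *That the endocrine rows permit resumption whatever the grade.* Several state no grade, but none says that grade is irrelevant, and Grade 2 or 3 hyperglycemia names Grade 1 or less as one route.
- *That a site could resume nivolumab after Grade 4 hyperglycemia on its own reading.* Medical Monitor approval is mandatory. What can vary is whether a site asks.
- *That the ambiguity generally decides whether both drugs stop.* The mandatory CMP-001 stop follows only from permanent nivolumab discontinuation for an immune-related event. The footnote conflict reaches discontinuation only indirectly, if a delay passes 12 weeks and no exception applies.

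**Conclusion.** The point holds as an internal inconsistency in two parts. One row, Grade 4 hyperglycemia, has an action and a clarification that do not fit together. Separately, footnote b differs from the row-level resume criterion in 17 of 23 delay cells, or 15 once the hepatic cells are set aside, with no stated precedence. The count relies on the footnote markers as they appear in the extracted text.

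The effect is limited. Sample size, power and type I error are untouched. Enrollment closed with 20 randomized subjects, and the SAP makes all analyses exploratory. It is still worth correcting: the table governs subject safety, the SAP lets enrolled subjects continue treatment to the 2-year cutoff, and in arms of 9 and 11 a single reclassified discontinuation is visible. The documents do not show that any subject was affected.

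**What to change.** 1. Reconcile the action and clarification cells for Grade 4 hyperglycemia so that they state one rule. If the clarification is meant as an exception, label it as one.
2. Make footnote b and each row's resume criterion agree, or add a sentence saying which prevails. Confirm where footnote c attaches.
3. Make Section 5.1.4.1 state that order of precedence, so that it no longer only points back to Table 2.

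Which clinical rule applies in each row is for the sponsor's medical team; no view is taken here. The cost is a protocol clarification letter or a short amendment. The planned analyses need no change.
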